1. STUDY SUMMARY

Protocol Title	A randomized, double-blind, placebo-controlled study of ALPN-101 in systemic lupus erythematosus
Protocol Number	AIS-A03
Investigational Phase	2
Investigational Product	ALPN-101 Injection
Study Sites	Approximately 75 international sites
Sample Size	At least 130 subjects
Study Duration	Each subject will participate for up to 34 weeks, including a Screening period of up to 6 weeks, a 24-week Treatment period, and a 4-week Follow-up period.
Study Population	Adults 18 to 70 years of age, inclusive, with active systemic lupus erythematosus (SLE)
Study Design	This is a Phase 2, multinational, multicenter, randomized, double-blind, placebo-controlled, parallel group study to evaluate the safety, tolerability, efficacy, immunogenicity, pharmacokinetics (PK), of ALPN-101 in adults with moderate to severe active SLE. After signing the Informed Consent Form (ICF), subjects will be evaluated during a Screening period of up to 42 days. Screening laboratory evaluations will be performed; assessment of disease activity will be performed by the Investigator and reviewed by the Sponsor or designee to confirm eligibility. Subjects will return to the clinic on Day 1 and undergo Baseline procedures, including assessment and confirmation of disease activity by the Investigator. Subjects who continue to meet eligibility criteria will be randomized 1:1 to receive blinded study drug once every 2 weeks (Q2W) for a total of 12 doses of: (1) 3 mg/kg ALPN-101 or (2) Placebo
	Baseline medications that are used for the treatment of SLE (i.e., hydroxychloroquine/hydroxychloroquine-like drugs, corticosteroids, immunosuppressants) must be maintained at stable doses through the Day 169 assessments, except for incidences of toxicity, for a protocol-permitted short-term increase (burst and taper) of corticosteroid dose in response to increased disease activity, or discretionary reduction in corticosteroids (taper) after Day 85 in the context of improvement in disease activity. Assessments of safety, efficacy, PK, anti-drug antibodies (ADA), and will be performed throughout the study. Refer to the Schedule of Procedures and Assessments (Table 1). Cumulative safety data will be reviewed at intervals by the Data Monitoring Committee (DMC), which will provide recommendations regarding study conduct, if indicated.

Primary Objectives	• To evaluate the safety and tolerability of ALPN-101 compared to placebo in subjects with chronic, moderate to severe active SLE	
Secondary Objectives	 To evaluate the efficacy of ALPN-101 in subjects with active SLE To assess the PK of ALPN-101 in subjects with active SLE To assess the incidence of ADA against ALPN-101 in subjects with active SLE 	
Summary of Key Inclusion Criteria	 Males and females, age 18 through 70 years, inclusive, at Screening Diagnosis of SLE for ≥ 6 months prior to Screening, as defined in §5.1 Positive anti-nuclear antibodies (ANA) (≥ 1:80) and/or elevated anti-double-stranded DNA (dsDNA) and/or elevated anti-Smith antibody test 	
	 Active SLE as defined in §5.1 at Screening as confirmed by Sponsor or designee, and at Baseline (i.e., prior to randomization on Day 1) as confirmed by Investigator Stable, appropriate standard of care for SLE, as described in §5.1 	
Summary of Key Exclusion Criteria	 Life-threatening or organ system-threatening SLE activity, that is sufficiently active that it is expected to require increase in treatment during the study 	
	 Proteinuria consistent with nephrotic syndrome: ≥ 3.5 g proteinuria/day, estimated based on urine protein-creatinine ratio (UPCR) ≥ 350 mg/mmol at Screening 	
	 Active lupus-related neuropsychiatric disease (with the exceptions of mild stable lupus headache, fatigue, mild stable organic brain syndrome) Drug-induced lupus 	
	 Evidence of active infection or risk or history of serious infection with tuberculosis; hepatitis B, hepatitis C; HIV Evidence of active infection with SARS-CoV-2 	
Study Drug Administration	ALPN-101 or matching placebo will be administered by intravenous (IV) infusion via an infusion pump over approximately 30 minutes; study drug will be given Q2W for 12 total doses.	
Primary Endpoints and Assessments	Safety and tolerability will be assessed by evaluating the type, frequency, severity, and seriousness of adverse events, including clinically significant changes in symptoms, physical exam findings, vital signs, laboratory tests (hematology, serum chemistries and coagulation, urinalysis), and electrocardiograms. Additional laboratory assessments and/or documentation may be collected as needed for characterization of adverse events of interest (AEIs).	
Efficacy Endpoints and Assessments	Efficacy endpoints will be assessed by evaluating disease activity relative to baseline and across treatment groups using the tools and assessments listed below, and derivatives calculated from them (e.g., SLE Responder Index [SRI] -4, -5, -6 response; time to and proportion with flare of SLE; others).	

Global Disease Activity Assessment Tools: British Isles Lupus Assessment Group index (BILAG) 2004 Systemic Lupus Erythematosus Disease Activity Index 2000 (SLEDAI-2K); SLEDAI-2K 30-Day (SLEDAI-2K 30) Physician's Global Assessment of SLE Disease Activity (PhGA) Patient Reported Outcomes and Quality of Life Assessment tools: Patient's Global Assessment of Disease Activity (PtGA) Short Form-36 (SF-36) health survey Functional Assessment of Chronic Illness Therapy-Fatigue (FACIT-F) (13-item) Clinical Biomarkers of SLE Activity: High-sensitivity C-reactive protein (hsCRP) Complement levels: C3, C4, CH50 Anti-dsDNA antibodies Corticosteroids: Dose of oral and parenteral corticosteroids **Pharmacokinetic** Serum concentrations of ALPN-101 will be measured. Pharmacokinetic endpoints include estimates of maximum concentration (C_{max}), area under **Endpoints and** the concentration-time curve (AUC), and trough concentration (Ctrough) at the Assessments end of dosing intervals. A population PK approach may be used to characterize the PK of ALPN-101 in SLE subjects. The presence and titer of ADA against ALPN-101 will be assessed at **Immunogenicity Endpoints** and Baseline (prior to study drug administration on Day 1) and at intervals throughout the study. Samples confirmed positive for ADA may be explored Assessments for neutralizing capacity. The relationship between ADA and PK will be analyzed; relationship between ADA and clinical outcomes may be explored. Randomization: Subjects will be randomized 1:1; randomization will be **Statistical** Considerations stratified by background immunosuppressive therapy and geographic region. Subjects who are randomized but do not receive study drug may be replaced.

Sample Size: A sample size of approximately 130 (~65 subjects/arm) will provide approximately 83–88% power (chi square two-sided test, alpha 0.05) to detect an absolute increase of 25% compared to placebo in the proportion of responders (e.g., as assessed by SRI-4 at Day 169) in the active treatment group, assuming a placebo response rate of 20–40%.

Statistical Methods:

All safety data will be summarized descriptively by treatment group and analyzed based on the safety population. Categorical safety endpoints will be summarized using incidence rates. The mean change from baseline, standard deviation, minimum, and maximum will be used to summarize continuous safety endpoints. No statistical inference is planned for the analysis of safety endpoints.

All efficacy endpoints will be summarized and analyzed for the modified Intent-to-Treat population. For categorical endpoints, the number and proportion of subjects in each category will be presented by treatment group. Proportions of subjects achieving response will be compared using a Cochran-Mantel-Haenszel test adjusted for randomization stratification factors. An estimate of the difference in proportions and corresponding 95% confidence interval. P-value will be presented for efficacy endpoints of primary interest. For continuous endpoints, the mean, standard deviation, median, minimum, and maximum will be presented by treatment group. For continuous endpoints with multiple post-Baseline visits, the treatment effect will be assessed through Mixed-effect Model Repeated Measures (MMRM) based on observed data. Difference in least-squares means will be derived using an analysis of covariance model controlling for stratification factors and baseline scores. For each treatment comparison, an estimate of the difference in least-squares means, and corresponding 95% confidence interval will be presented.

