3. STUDY OBJECTIVES

3.1. Primary Objective

The primary objective of this study is to evaluate the safety and tolerability of ALPN-101 compared to placebo in subjects with chronic, moderate to severe active SLE.

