4.4.2. Justification of Study Design

The study will be randomized, placebo-controlled, and blinded to minimize bias in reporting of safety events, partially-subjective disease activity measures, and patient-reported outcomes.

Randomization will be stratified by use of concomitant oral immunosuppressive therapy; stratification will reduce the risk that the safety assessment of ALPN-101 may be confounded by imbalance in SOC agents that carry their own risks of AEs.

Randomization also will be stratified by geographic region.

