4.4.4. Justification of Endpoints

This is the first clinical investigation to evaluate ALPN-101 in patients with active SLE, and the first clinical investigation of dosing over a duration of greater than 4 weeks. Therefore, the primary objective is safety and tolerability which will be assessed by the type, frequency, severity, and seriousness of AEs, including clinically significant changes in symptoms, physical exam findings, vital signs, laboratory tests (hematology, serum chemistries, coagulation and urinalysis), and ECGs, and will be evaluated by comparison to placebo. Additional assessments and/or documentation will be collected for SAEs and may be collected for adverse events of interest (AEIs) related to mechanism of action (i.e., infections), mode of administration (e.g., infusion reactions), or observations in completed and ongoing trials (e.g., aphthous ulcers).

A secondary objective is to evaluate the efficacy of ALPN-101 based on change in disease activity compared to placebo. The measurement of disease activity in SLE involves an assessment of characteristic signs and symptoms across multiple organ systems, along with the results of laboratory parameters. Multiple tools for assessment of global disease activity have been developed. The present study employs the Systemic Lupus Erythematosus Disease Activity Index 2000 (SLEDAI-2K) and SLEDAI-2K 30-Day (SLEDAI-2K 30), British Isles Lupus Assessment Group index (BILAG) 2004, the Patient's Global Assessment of Disease Activity (PtGA), and a Physician's Global Assessment of SLE Disease Activity (PhGA). The data from these tools can be used alone or combined as responder indices to measure efficacy.

To gain a broad understanding of the potential impact of the novel mechanisms of ALPN-101 on SLE activity, change from baseline over time and comparison to placebo in results of several other assessments will be explored. These include assessments that may be more sensitive to change in selected organ systems (Cutaneous Lupus Erythematosus Disease Area and Severity Index [CLASI] for mucocutaneous disease;

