7.8. Analysis of Safety Endpoints

The primary study objective of assessing safety and tolerability of ALPN-101 in subjects with active SLE will be assessed using TEAEs, AEIs, SAEs, physical exam findings, vital signs, ECG measurements, and laboratory tests. All safety data will be descriptively summarized by treatment group. No formal inference is planned. Analyses will be based on subjects in the safety population. Individual subjects will only be counted once when calculating the incidence of AEs.

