7.8.1. Treatment-Emergent Adverse Events

AEs will be recorded at all scheduled and unscheduled visits during the study. Summaries will be presented for TEAEs. In this study, signs and symptoms of SLE activity are captured in the disease activity assessments and will not be reported as AEs. Clinically significant changes in physical exam findings, laboratory test results, and ECG results will be recorded and analyzed as AEs. The incidence, seriousness, and severity of TEAEs and the relationship of the events to study drug will be used to assess safety.

All AEs terms will be classified using MedDRA and reported based on system organ classes and preferred terms. Adverse event severity will be graded using Common Terminology Criteria for Adverse Events (CTCAE), version 5.0. AEIs will be reviewed by the medical monitor lead.

In general, the incidence of AEs will be summarized by the number and the percentage of unique subjects in the safety population who experiencing an event. As such, subjects who report the

same event on multiple occasions will only be counted once. A by-subject listing of all AEs reported will be provided. Rules for the imputation of missing and partial AE dates and missing designations of AE severity, relatedness and seriousness are defined in Section 13.

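### The primary objective is safety compared with placebo, but the plan pre-specifies no between-arm difference or interval for any safety endpoint

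*Protocol*

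**What the plan says.** Protocol 3.1 sets a comparative question: "The primary objective of this study is to evaluate the safety and tolerability of ALPN-101 compared to placebo". Protocol 4.4.4 lists the safety measures and adds that safety is to be assessed against the control arm: "and will be evaluated by comparison to placebo".

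The analysis sections stop short of a comparison. Protocol section 1 (Statistical Methods) says "No statistical inference is planned for the analysis of safety endpoints". SAP 7.8 says "All safety data will be descriptively summarized by treatment group. No formal inference is planned". For adverse events, SAP 7.8.1 specifies that "the incidence of AEs will be summarized by the number and the percentage of unique subjects in the safety population". Protocol 10.5.5 and SAP 7.8.2 to 7.8.5 add by-arm descriptive statistics, graded laboratory abnormalities, shift tables, and vital-sign and ECG categories. Neither document plans a risk difference, risk ratio or confidence interval for any safety endpoint, including the three adverse events of interest (AEIs) in SAP 3.2: infusion-related reactions, oral mucocutaneous lesions, and infections of Grade 3 or higher.

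Efficacy is treated differently. It is a secondary objective (Protocol 3.2), and Protocol 10.2 and SAP 4.2 say the sample size was not derived for formal efficacy testing. Even so, SAP 7.4.1 provides treatment differences with 95% intervals, and SAP 7.5.1 and 7.6 apply them.

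SAP 4.1 records that 130 subjects were expected and that enrolment stopped at 76.

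**The concern.** The secondary question gets an estimate of the treatment difference and its precision; the primary question gets neither. The plan evidently regards interval estimates as suitable without a powered hypothesis, since it uses them for efficacy, so lack of power does not explain leaving them out for safety.

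At about 38 per arm, the AEIs may be few. A table row showing no events in either arm, or one against two, does not show how large an excess remains compatible with the data. Protocol 2.7 calls the drug potentially immunosuppressive, with a possible increase in infection risk, so for Grade 3 or higher infections that is the figure a reader needs. Intervals that readers derive for themselves after unblinding also leave the choice of events and method open until the results are known. A short list fixed beforehand closes that choice.

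**Working it through.** **1. The plan's own figures.** The documents give no power or precision figure for safety, so only the efficacy power can be reproduced. With n = 65 per arm, two-sided alpha 0.05 and a pooled-variance chi-square test, power = Φ[(Δ − 1.96·SE0)/SE1], where SE0 = √(2p̄(1−p̄)/n) and SE1 = √((p1(1−p1) + p2(1−p2))/n).

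- SRI-4, 40% v 65%: SE0 = √(2 × 0.525 × 0.475/65) = 0.0876; SE1 = √((0.24 + 0.2275)/65) = 0.0848; Φ(0.923) = 82.2%. Stated: 82%.
- BICLA (called BILAG in Protocol 10.2), 20% v 45%: SE0 = √(2 × 0.325 × 0.675/65) = 0.0822; SE1 = √((0.16 + 0.2475)/65) = 0.0792; Φ(1.124) = 86.9%. Stated: 87%.

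Both reproduce.

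**2. Inputs for the safety comparison.** The planned size is 65 per arm (Protocol 10.2). Actual enrolment is 76 (SAP 4.1); with 1:1 allocation this is taken as 38 per arm, which is an assumption because the split is not given. The documents state no expected safety event rates in SLE, so all event counts below are illustrative. The only AEI rate on drug in the documents is 5 of 66 healthy volunteers with aphthous ulcers (Protocol 8.1.2), or 5/66 = 7.6%; 0.076 × 38 ≈ 3 subjects.

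**3. No events in either arm.** The Miettinen-Nurminen limit solves (d̂ − δ)²/V(δ) = z², where V(δ) is the variance at the estimates restricted to p1 − p2 = δ, multiplied by 2n/(2n−1). With zero events and δ > 0, the restricted estimates are p2 = 0 and p1 = δ. The equation becomes δ(2n−1)/(2(1−δ)) = z², so δ = 2z²/(2n − 1 + 2z²). With z² = 3.84:

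- n = 38: 7.68/(75 + 7.68) = 9.3%, giving −9.3 to +9.3 points.
- n = 65: 7.68/(129 + 7.68) = 5.6%, giving −5.6 to +5.6 points.

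**4. Other illustrative counts, 38 per arm** (same method, solved numerically; ALPN-101 v placebo):

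| Events | Risk difference (points) | 95% CI |
|---|---|---|
| 2 v 1 | 1/38 = +2.6 | −9.0 to +15.1 |
| 3 v 0 | 3/38 = +7.9 | −1.8 to +20.9 |

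**5. Check by a second method.** With zero events in both arms, the Newcombe (Wilson-score) limit is z²/(n + z²): 3.84/41.84 = 9.2% at n = 38 and 3.84/68.84 = 5.6% at n = 65. For 3 v 0 it gives −2.6 to +20.8. The two methods agree within one point.

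**The case against.** The strongest defence is that descriptive safety reporting is a deliberate and openly stated choice. The protocol and SAP agree. This is an early-phase study and the first in SLE. Safety is to be judged on the type, frequency, severity and seriousness of events, and a data monitoring committee reviews cumulative safety data. All of this stands: there is no contradiction and no wrong number.

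Three stronger readings are tempting and are not supported.

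- A reader might infer that the plan forbids any between-arm estimate. It does not. SAP 7.8 says "No formal inference is planned", which leaves inference unplanned, not prohibited, and a descriptive point difference is not inference.
- A reader might infer that the trial cannot say what excess risk it shows. By-arm counts and percentages are planned, so the crude difference is one subtraction away, and an unstratified interval follows from the same counts, as the working shows. What is missing is a pre-specified display.
- A reader might take Protocol 4.4.2, where "stratification will reduce the risk that the safety assessment of ALPN-101 may be confounded by imbalance in SOC agents", as promising a stratified safety analysis. It justifies stratified randomization, which serves that purpose at allocation. It neither promises nor requires stratification in the safety tables.

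Two further cautions hold. An interval shows imprecision without reducing it. The oral-lesion illustration borrows a healthy-volunteer rate and assumes no placebo events, although Protocol 8.1.2 lists other causes of such lesions. It shows scale and is not a forecast.

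**Conclusion.** The point holds as a gap between a comparative primary objective and an analysis that pre-specifies no comparison. The planned safety output will not state what excess risk is compatible with the data. For an event seen in neither arm, that range is −9.3 to +9.3 points at 38 per arm, against −5.6 to +5.6 at the planned 65. These figures rest on an even 38/38 split, on all 76 subjects entering the safety population, and on assumed event counts.

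This is a cheap improvement to reporting, not an error that undermines the trial. The defence does not remove the reason to act, because intervals derived after unblinding leave the events and the method to be chosen with the results in view.

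**What to change.** In SAP 7.8.1, for a short fixed list (each of the three AEIs, SAEs, and any TEAE), add the ALPN-101 minus placebo risk difference with a Miettinen-Nurminen 95% CI. Name one method in advance, with no switch that depends on the data. It can be unstratified, or weighted by Mantel-Haenszel over the two-level background-immunosuppressant stratum. The weighted difference, Σw(p1 − p2)/Σw with w = n1·n2/(n1 + n2) in each stratum, stays estimable when a stratum has no events: that stratum contributes a zero difference with its usual weight. No unstratified fallback is needed.

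Amend SAP 7.8 to say that no formal hypothesis testing is planned and that confidence intervals are descriptive; otherwise the new intervals would sit awkwardly with the present sentence. Give no p-values. No protocol edit is needed, because Protocol 10.1 gives the SAP precedence. Since Protocol 10.1 also asks for deviations to be set out in the SAP, a line in SAP section 8 should record the addition. Make the change before the database is unblinded.

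The cost is a few table columns and a few SAP sentences, with no new data. The downside is that the intervals will be wide and unadjusted for multiplicity, and the table footnote should say so.

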2. BACKGROUND

2.1. Systemic Lupus Erythematosus

Systemic lupus erythematosus (SLE) is an autoimmune disease that affects 0.01% to 0.2% of people worldwide, and is characterized by failures of immune self-tolerance, with the generation of pathogenic subsets of lymphocytes and autoantibodies that disrupt the function of cells and homeostatic systems and mediate tissue injury in multiple organs. Etiology remains incompletely defined; there is evidence that genetic, epigenetic, environmental, immunologic, and hormonal factors may contribute to disease susceptibility and severity (1-5).

Clinically, lupus is characterized by periods of remission and relapse of constitutional and organ-specific signs and symptoms that are highly variable across populations and can change over time in individual patients. The most common clinical features include fever, debilitating fatigue, joint inflammation, skin and mucosal lesions, serositis, hematologic disorders including anemia, leukopenia or thrombocytopenia, and lupus nephritis. The latter is the most common life- and organ-threatening manifestation of SLE, estimated to impact 40% to 70% of patients, with progression to renal failure in 10% to 20% (6, 7). Less common but serious SLE manifestations include neuropsychiatric, demyelinating and neurovascular disease, and antiphospholipid antibody syndrome with venous thrombosis, arterial occlusion and/or fetal loss. Most other organ systems can also be involved (8-17).

Therapeutic management is tailored to the severity of disease and organ systems involved. Practice guidelines and consensus statements have been developed for treatment of SLE, lupus nephritis, and other organ-specific manifestations, and are revised at regular intervals to incorporate emerging data (18-20). Current standard of care (SOC) includes antimalarial agents for treatment of skin disease to reduce risk of flare in all patients, nonsteroidal anti-inflammatory drugs (NSAIDs) for management of headache and musculoskeletal pain, and corticosteroids for rapid reduction of inflammation and management of fatigue. Oral immunosuppressive agents (e.g., methotrexate, azathioprine, mycophenolate and others) are used to reduce dependence on corticosteroids and to address more persistent manifestations. Belimumab, an inhibitor of B cell growth factors, has been approved for use in refractory SLE and B cell depletion with rituximab is indicated for immune thrombocytopenia, including that arising in SLE, with benefit reported in other manifestations. High dose corticosteroids and cytotoxic agents (e.g., cyclophosphamide) are used for serious manifestations refractory to other agents. Initial treatment for clinically significant lupus nephritis comprises corticosteroids together with cyclophosphamide, azathioprine or mycophenolate. For lupus nephritis refractory to initial therapy, selective inhibition of the T cell-mediated immune response through the addition of calcineurin inhibitors has demonstrated benefit (21).

Despite earlier diagnosis and improved treatment regimens, more than 60% of patients with access to current best standards of medical care develop clinically-detectable organ damage within 2 to 7 years (22). A recent meta-analysis involving over 27,000 patients with SLE reported a 3-fold increase in the risk of death compared with the general population, primarily due to cardiovascular disease (23). Toxicity associated with corticosteroids and immunosuppression contributes substantially to the burden of disease: corticosteroid use is associated with loss of bone integrity and development of metabolic syndrome, contributing to cardiovascular disease; broad spectrum immunosuppressants increase the risk of serious infection and neoplasm, and use of calcineurin inhibitors is limited by nephrotoxicity. There is a continuing need to develop pharmacologic interventions that more specifically target pathogenic pathways, with the goal of improving efficacy while limiting toxicity.

